8. STUDY ASSESSMENTS AND PROCEDURES

The investigator (or an appropriate delegate at the investigator site) must obtain a signed and dated ICD before performing any study specific procedures.

Study procedures and their timing are summarized in the [SoA](#). Protocol waivers or exemptions are not allowed.

Safety issues should be discussed with the sponsor immediately upon occurrence or awareness to determine whether the participant should continue or discontinue study intervention.

Adherence to the study design requirements, including those specified in the [SoA](#), is essential and required for study conduct.

All screening evaluations must be completed and reviewed to confirm that potential participants meet all eligibility criteria. The investigator will maintain a screening log to record details of all participants screened and to confirm eligibility or record reasons for screening failure, as applicable.

Participants will be screened within 28 days prior to administration of the study intervention to confirm that they meet the study population criteria for the study. If the time between screening and dosing exceeds 28 days as a result of unexpected delays (eg, delayed drug shipment), then participants do not require rescreening if the laboratory results obtained prior to first dose administration meet eligibility criteria.

A participant who qualified for this protocol but did not enroll from an earlier cohort/group may be used in a subsequent cohort/group without rescreening, provided laboratory results obtained prior to the first dose administration meet eligibility criteria for this study. In addition, other clinical assessments or specimen collections, eg, banked biospecimens, may be used without repeat collection, as appropriate.

Every effort should be made to ensure that protocol required tests and procedures are completed as described. However, it is anticipated that from time to time there may be circumstances outside the control of the investigator that may make it unfeasible to perform the test. In these cases, the investigator must take all steps necessary to ensure the safety and well-being of the participant. When a protocol required test cannot be performed, the investigator will document the reason for the missed test and any corrective and preventive actions that he or she has taken to ensure that required processes are adhered to as soon as possible. The study team must be informed of these incidents in a timely manner.

If an IV catheter is utilized for blood sample collections, ECGs and vital sign assessments (pulse rate and BP) should be collected prior to the insertion of the catheter.

For samples being collected and shipped, detailed collection, processing, storage, and shipment instructions and contact information will be provided to the investigator site prior to initiation of the study.

The total blood sampling volume for individual participants in this study is approximately 380 mL. The actual collection times of blood sampling may change. Additional blood samples may be taken for safety assessments at times specified by Pfizer, provided the total volume taken during the study does not exceed 550 mL during any period of 56 consecutive days.

To prepare for study participation, participants will be instructed on the information in the [Lifestyle Considerations](#) and [Concomitant Therapy](#) sections of the protocol.

8.1. Efficacy Assessments

Not applicable.

8.2. Safety Assessments

Planned time points for all safety assessments are provided in the [SoA](#). Unscheduled clinical laboratory measurements may be obtained at any time during the study to assess any perceived safety issues.

8.2.1. Physical Examinations

A complete physical examination will include, at a minimum, head, ears, eyes, nose, mouth, skin, heart and lung examinations, lymph nodes, and gastrointestinal, musculoskeletal, and neurological systems.

A brief physical examination will include, at a minimum, assessments of general appearance, the respiratory and cardiovascular systems, and participant reported symptoms.

Physical examinations may be conducted by a physician, trained physician's assistant, or nurse practitioner as acceptable according to local regulation.

Height and weight will also be measured and recorded as per the [SoA](#). For measuring weight, a scale with appropriate range and resolution is used and must be placed on a stable, flat surface. Participants must remove shoes, bulky layers of clothing, and jackets so that only light clothing remains. They must also remove the contents of their pockets and remain still during measurement of weight.

Physical examination findings collected during the study will be considered source data and will not be required to be reported, unless otherwise noted. Any untoward physical examination findings that are identified during the active collection period and meet the definition of an AE or SAE ([Appendix 3](#)) must be reported according to the processes in [Sections 8.3.1 to 8.3.3](#).

8.2.2. Vital Signs

Supine BP will be measured with the participant's arm supported at the level of the heart and recorded to the nearest mm Hg after approximately 5 minutes of rest. The same arm (preferably the dominant arm) will be used throughout the study. Participants should be instructed not to speak during measurements.

The same properly sized and calibrated BP cuff will be used to measure BP each time. The use of an automated device for measuring BP and pulse rate is acceptable; however, when done manually, pulse rate will be measured in the brachial/radial artery for at least 30 seconds. When the timing of these measurements coincides with a blood collection, BP and pulse rate should be obtained prior to the nominal time of the blood collection.

Additional collection times, or changes to collection times, of BP and pulse rate will be permitted, as necessary, to ensure appropriate collection of safety data.

8.2.2.1. Respiratory Rate

Not applicable.

8.2.2.2. Temperature

Not applicable.

8.2.3. Electrocardiograms

Standard 12-lead ECGs utilizing limb leads (with a 10 second rhythm strip) should be collected at times specified in the **SoA** section of this protocol using an ECG machine that automatically calculates the heart rate and measures PR, QT, and QTc intervals and QRS complex. Alternative lead placement methodology using torso leads (eg, Mason-Likar) should not be used given the potential risk of discrepancies with ECGs acquired using standard limb lead placement. All scheduled ECGs should be performed after the participant has rested quietly for at least 5 minutes in a supine position.

To ensure the safety of the participants, a qualified individual at the investigator site will make comparisons to baseline measurements. Additional ECG monitoring will occur if a) a post dose QTcF interval is increased by ≥ 60 msec from the baseline **and** is > 450 msec; or b) an absolute QT value is ≥ 500 msec for any scheduled ECG. If either of these conditions occurs, then 2 additional ECGs will be collected approximately 2 to 4 minutes apart to confirm the original measurement. If the QTc values from these repeated ECGs remain above the threshold value, then a single ECG must be repeated at least hourly until QTc values from 2 successive ECGs fall below the threshold value that triggered the repeat measurement.

If a) a post dose QTcF interval remains ≥ 60 msec from the baseline **and** is > 450 msec; or b) an absolute QT value is ≥ 500 msec for any scheduled ECG for greater than 4 hours (or sooner, at the discretion of the investigator); or c) QTcF intervals get progressively longer, the participant should undergo continuous ECG monitoring. A cardiologist should be consulted if QTcF intervals do not return to less than the criteria listed above after 8 hours of monitoring (or sooner, at the discretion of the investigator).

In some cases, it may be appropriate to repeat abnormal ECGs to rule out improper lead placement as contributing to the ECG abnormality. It is important that leads be placed in the same positions each time in order to achieve precise ECG recordings. If a machine read QTc value is prolonged, as defined above, repeat measurements may not be necessary if a

qualified medical provider's interpretation determines that the QTcF values are in the acceptable range.

ECG values of potential clinical concern are listed in [Appendix 7](#).

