9.3.4.1. Electrocardiogram Analyses

Changes from baseline for the ECG parameters QT interval, heart rate, QTc interval, PR interval, and QRS complex will be summarized by treatment and time.

The number (%) of participants with maximum postdose QTc values and maximum increases from baseline in the following categories will be tabulated by treatment:

Safety QTc Assessment

Degree of Prolongation	Mild (msec)	Moderate (msec)	Severe (msec)
Absolute value	>450-480	>480-500	>500
Increase from baseline		30-60	>60

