10.7. Appendix 7: ECG Findings of Potential Clinical Concern

ECG Findings That May Qualify as AEs

 Marked sinus bradycardia (rate <40 bpm) lasting minutes. New PR interval prolongation >280 msec. New prolongation of QTcF to >480 msec (absolute) or by \geq60 msec from baseline. New onset- atrial flutter or fibrillation, with controlled ventricular response rate: ie, rate <120 bpm. New onset type I second degree (Wenckebach) AV block of >30 seconds' duration. Frequent PVCs, triplets, or short intervals (<30 seconds) of consecutive ventricular complexes.
ECG Findings That May Qualify as SAEs

 QTcF prolongation >500 msec. New ST-T changes suggestive of myocardial ischemia. New onset left bundle branch block (QRS >120 msec). New onset right bundle branch block (QRS >120 msec). Symptomatic bradycardia. Asystole: 
 In awake, symptom free participants in sinus rhythm, with documented periods of asystole \geq3.0 seconds or any escape rate <40 bpm, or with an escape rhythm that is below the AV node. In awake, symptom free participants with atrial fibrillation and bradycardia with 1 or more pauses of at least 5 seconds or longer. Atrial flutter or fibrillation, with rapid ventricular response rate: rapid = rate >120 bpm. Sustained supraventricular tachycardia (rate >120 bpm) ("sustained" = short duration with relevant symptoms or lasting >1 minute).

- Ventricular rhythms >30 seconds' duration, including idioventricular rhythm (heart rate <40 bpm), accelerated idioventricular rhythm (HR >40 bpm to <100 bpm), and monomorphic/polymorphic ventricular tachycardia (HR >100 bpm (such as torsade's de pointes)).
- Type II second-degree (Mobitz II) AV block.
- Complete (third-degree) heart block.

ECG Findings That Qualify as SAEs

- Change in pattern suggestive of new myocardial infarction.
- Sustained ventricular tachyarrhythmias (>30 seconds' duration).
- Second or third-degree AV block requiring pacemaker placement.
- Asystolic pauses requiring pacemaker placement.
- Atrial flutter or fibrillation with rapid ventricular response requiring cardioversion.
- Ventricular fibrillation/flutter.
- At the discretion of the investigator, any arrhythmia classified as an adverse experience.

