## 8. APPENDICES

### Appendix 1. Categorical Classes for ECG and Vital Signs of Potential Clinical Concern

#### Categories for QTcF

Degree of Prolongation	Mild (msec)	Moderate (msec)	Severe (msec)
Absolute value	>450-480	>480-500	>500
Increase from baseline		30-60	>60

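### Protocol 8.2.3 sets its absolute ECG trigger on uncorrected QT, so read literally a narrow band of postdose QTcF values of 501-509 msec prompts no repeat ECG above about 60-63 bpm (low priority)

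*Protocol*

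**What the plan says.** Protocol section 8.2.3 has two triggers for repeat ECGs. Limb (a) is a postdose QTcF at least 60 msec above baseline and above 450 msec. Limb (b) is "an absolute QT value is ≥ 500 msec for any scheduled ECG". The continuous-monitoring rule uses the uncorrected interval again: "an absolute QT value is ≥ 500 msec for any scheduled ECG for greater than 4 hours".

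The other steps in the section use the corrected interval:

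- Confirmation, leading to hourly repeats: "If the QTc values from these repeated ECGs remain above the threshold value". Release from the hourly repeats is also judged on QTc, against the threshold that triggered.
- Referral: "A cardiologist should be consulted if QTcF intervals do not return to less than the criteria listed above after 8 hours of monitoring".
- The provision for a clinician's over-read begins "If a machine read QTc value is prolonged, as defined above".

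Elsewhere, Appendix 7 (section 10.7) lists "QTcF prolongation >500 msec" among findings that may qualify as SAEs. Section 9.3.4.1 tabulates "The number (%) of participants with maximum postdose QTc values", with above 500 msec as severe. SAP Appendix 1 uses the same cut-offs under "Categories for QTcF".

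**The concern.** QT and QTcF agree only at 60 bpm. Above that rate QTcF is the larger, so a limit of 500 msec on QT is reached later than one of 500 msec on QTcF. Limb (a) catches most such ECGs through the change from baseline, but not when baseline is already close to the eligibility ceiling. An ECG that the protocol itself lists as a possible SAE could then fall outside a mandatory rule for repeats.

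The rule is also hard to run as printed. If limb (b) fires on QT, the decision to continue or stop compares QTc with a cut-off that was set on QT.

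**Working it through.** The plan states no figure on this point, so there is none to reproduce.

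**Inputs**
- Limbs (a) and (b): protocol 8.2.3.
- Correction formula: SAP 3.5.4, QTcF = QT/RR^(1/3) with RR = 60/HR. Hence QTcF = QT × (HR/60)^(1/3).
- Highest baseline QTcF: 450 msec, from exclusion 18 (protocol 5.2). It is assumed that the baseline used in limb (a) also respects this limit.
- Half-life about 2 hours: protocol 2.2.4. ECG times: Schedule of Activities, where the Day 1 ECG is predose.

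**Step 1: where limb (a) is silent although QTcF exceeds 500.** This needs a rise below 60 msec, so baseline must exceed postdose QTcF minus 60. In whole msec, postdose 501 needs a baseline of 442 or more, and postdose 509 needs 450. Taking postdose 501, 502, ..., 509 in turn, the number of qualifying baselines is 9 + 8 + 7 + 6 + 5 + 4 + 3 + 2 + 1 = 45 pairs, with rises of 51-59 msec. With a baseline of 441 or below there are none. The ranges are joint: of the 9 × 9 = 81 combinations of baseline 442-450 with postdose 501-509, the other 36 rise by 60 msec or more and fire limb (a).

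**Step 2: where limb (b) is also silent.** QT falls below 500 when HR exceeds 60 × (QTcF/500)^3.

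| Postdose QTcF (msec) | Limb (b) silent above (bpm) |
|---|---|
| 501 | 60.36 |
| 503 | 61.09 |
| 505 | 61.82 |
| 509 | 63.30 |

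Pairs that fire neither limb, by heart rate: 0 at 60 bpm or below, 9 at 60.5, 17 at 61, 35 at 62, 44 at 63, and all 45 from 63.3 bpm.

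**Example.** Baseline 445, postdose QTcF 503 at 75 bpm. The rise is 58 msec. QT = 503/(75/60)^(1/3) = 467 msec. Neither limb fires.

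**Step 3: slow heart rates.** A QT of 500 msec corresponds to QTcF 454 at 45 bpm, 471 at 50 bpm and 486 at 55 bpm. So limb (b) as printed can fire on a QTcF well under 500. For instance, QT 505 at 56 bpm gives QTcF = 505 × (56/60)^(1/3) = 493.5. With baseline 440 the rise is 53.5, so limb (b) is the only limb that fires.

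**Step 4: exposure to the gap.** Each completer has one planned postdose ECG, on Day 3, so about 16 in all. At 48 hours that is 48/2 = 24 half-lives after dosing, and protocol Table 3 projects C48 as BQL at both study doses. Only an early-termination ECG could fall while drug is present.

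**The case against.** The strongest reply is that QT here is loose wording for QTc. Confirmation, release, referral and the over-read sentence all treat the limits as limits on a corrected interval. On that reading no ECG is missed and the change is editorial. The reading is plausible and cannot be excluded. However, the text prints QT twice, and exclusion 18 separates uncorrected QT from QTcF, so a site could reasonably apply limb (b) as written.

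The second reply is that such an ECG would not go unnoticed. A qualified individual compares each ECG with baseline (8.2.3), Appendix 7 findings are recommended as alerts, medically indicated supplemental measurements follow an AE or SAE (10.3.3), and QTc above 500 is tabulated. All of this stands. None of it requires the two prompt repeats or the hourly sequence. The further criterion of progressive QTcF lengthening needs serial ECGs and leads only to continuous monitoring.

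Two stronger readings are tempting and not supported. A reader might infer that participants are exposed to undetected drug-induced prolongation. The safeguards above, the narrow band and the Day 3 timing do not bear that out. A reader might also infer that replacing QT by QTcF in limb (b) is a free repair. It is not. The example of QT 505 at 56 bpm triggers now and would no longer do so, although Appendix 7 lists new QTcF prolongation above 480 msec as a possible AE. Counted as in Step 1 (baseline 450 or less, rise below 60), the replacement would remove 245 pairs with QTcF 481-499 at 55 bpm and 176 at 56 bpm. Pair counts are not probabilities, in either direction, but the loss is real.

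**Conclusion.** The point holds as a low-priority correction. Read literally, limb (b) is set on a different quantity from the limits around it, and 45 whole-msec pairs (baseline 442-450, postdose QTcF 501-509, rise 51-59) fire neither limb at heart rates above about 60-63 bpm.

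This rests on the literal reading and on a baseline of 450 msec or less. A Day 1 predose value above 450 would widen the gap. The documents give no basis for the probability of an affected ECG, and none is claimed. Practical impact is very small. ECG is neither the primary endpoint nor among the listed secondary endpoints, so no planned conclusion on occupancy, PK, TEAEs, laboratory tests or vital signs depends on it.

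**What to change.** In protocol 8.2.3, write limb (b) as an absolute QT or QTcF of 500 msec or more, in both the repeat-ECG rule and the continuous-monitoring rule. State that confirmation and release use the quantity that triggered: QTcF for a QTcF trigger, QT for a QT trigger. All 45 pairs then fire limb (b) at any heart rate, and every ECG that triggers today still does. Exclusion 18, Appendix 7 and the SAP need no change.

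The cost is a few extra unscheduled repeat ECGs, including hourly repeats for participants with slow heart rates whose QT stays at 500 msec or more. No scheduled ECG is added. The edit needs a protocol amendment with IRB/EC approval, and health-authority approval if classed as substantial (section 10.1.1), so it can wait for the next amendment.

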8.2.3.1. Continuous Cardiac Monitoring by Telemetry

Not applicable.

8.2.4. Clinical Safety Laboratory Assessments

See [Appendix 2](#) for the list of clinical safety laboratory tests to be performed and the [SoA](#) for the timing and frequency. All protocol-required laboratory assessments, as defined in [Appendix 2](#), must be conducted in accordance with the laboratory manual and the [SoA](#). Unscheduled clinical laboratory measurements may be obtained at any time during the study to assess any perceived safety issues.

The investigator must review the laboratory report, document this review, and record any clinically relevant changes occurring during the study in the AE section of the CRF. Clinically significant abnormal laboratory findings are those which are not associated with the underlying disease, unless judged by the investigator to be more severe than expected for the participant's condition.

All laboratory tests with values considered clinically significantly abnormal during participation in the study or within 28 to 35 calendar days after the last dose of study intervention should be repeated until the values return to normal or baseline or are no longer considered clinically significant by the investigator or medical monitor.

If such values do not return to normal/baseline within a period of time judged reasonable by the investigator, the etiology should be identified and the sponsor notified.

See [Appendix 6](#) for suggested actions and follow-up assessments in the event of potential drug-induced liver injury.

8.2.5. COVID-19 Specific Assessments

Participants will be tested for SARS-CoV-2 infection by PCR prior to being admitted to the clinic for confinement and a subsequent COVID-19 test will be performed after 4 days (ie, upon completion of 4 x 24 hours in house), or if they develop COVID-19 like symptoms. Additional testing may be required by local regulations or by the Principal Investigator.

8.2.6. Pregnancy Testing

Pregnancy tests may be urine or serum tests but must have a sensitivity of at least 25 mIU/mL. Pregnancy tests will be performed in WOCBP at the times listed in the [SoA](#). Following a negative pregnancy test result at screening, appropriate contraception must be commenced, and a second negative pregnancy test result will be required at the baseline visit prior to the participant's receiving the study intervention. Pregnancy tests will also be done

whenever 1 menstrual cycle is missed during the active treatment period (or when potential pregnancy is otherwise suspected) and at the end of the study. Pregnancy tests may also be repeated if requested by IRBs/ECs or if required by local regulations. If a urine test cannot be confirmed as negative (eg, an ambiguous result), a serum pregnancy test is required. In such cases, the participant must be excluded if the serum pregnancy result is positive.

8.2.7. Suicidal Ideation and Behavior Risk Monitoring

Not applicable.

8.3. Adverse Events, Serious Adverse Events, and Other Safety Reporting

The definitions of an AE and an SAE can be found in [Appendix 3](#).

AEs may arise from symptoms or other complaints reported to the investigator by the participant (or, when appropriate, by a caregiver, surrogate, or the participant's legally authorized representative), or they may arise from clinical findings of the Investigator or other healthcare providers (clinical signs, test results, etc.).

The investigator and any qualified designees are responsible for detecting, documenting, and recording events that meet the definition of an AE or SAE and remain responsible to pursue and obtain adequate information both to determine the outcome and to assess whether the event meets the criteria for classification as an SAE or caused the participant to discontinue Ritlecitinib (see [Section 7.1](#)).

During the active collection period as described in [Section 8.3.1](#), each participant (or, when appropriate, by a caregiver, surrogate, or the participant's legally authorized representative) will be questioned about the occurrence of AEs in a nonleading manner.

In addition, the investigator may be requested by Pfizer Safety to obtain specific follow-up information in an expedited fashion.

8.3.1. Time Period and Frequency for Collecting AE and SAE Information

The time period for actively eliciting and collecting AEs and SAEs (“active collection period”) for each participant begins from the time the participant provides informed consent, which is obtained before the participant’s participation in the study (ie, before undergoing any study related procedure and/or receiving study intervention), through and including a minimum of 28 calendar days, except as indicated below, after the last administration of the study intervention.

Follow-up by the investigator continues throughout and after the active collection period and until the AE or SAE or its sequelae resolve or stabilize at a level acceptable to the investigator.

For participants who are screen failures, the active collection period ends when screen failure status is determined.

If the participant withdraws from the study and also withdraws consent for the collection of future information, the active collection period ends when consent is withdrawn.

If a participant permanently discontinues or temporarily discontinues study because of an AE or SAE, the AE or SAE must be recorded on the CRF and the SAE reported using the CT SAE Report Form.

Investigators are not obligated to actively seek information on AEs or SAEs after the participant has concluded study participation. However, if the investigator learns of any SAE, including a death, at any time after a participant has completed the study, and he/she considers the event to be reasonably related to the study intervention, the investigator must promptly report the SAE to Pfizer using the CT SAE Report Form.

